7.7 Follow-up of Adverse Events

All AEs will be followed with appropriate medical management until resolved. All AEs that occur prior to the post-surgery follow-up visit should be recorded. Patients with an AE of Grade >1 will be followed until the resolution of the AE to Grade 0 to 1 or until the beginning of a new anticancer therapy, whichever occurs first. Serious AEs that occur within 90 days of the end of treatment or before initiation of a new anticancer treatment should also be followed and recorded.

Patients removed from study for unacceptable AEs will be followed until resolution or stabilization of the AE. For selected AEs for which administration of the investigational drug was stopped, a re-challenge of the patient with the investigational drug may be conducted if considered both safe and ethical by the Investigator.

7.8 Adverse Events Monitoring

All AEs, whether or not unexpected, and whether or not considered to be associated with the use of the study drug, will be entered into OnCore®, as noted above.

The Investigator will assess all AEs and determine reportability requirements to the UCSF Data and Safety Monitoring Committee (DSMC) and UCSF's Institutional Review Board, the IRB; and, when the study is conducted under an IND, to the FDA if it meets the FDA reporting criteria.

All AEs entered into OnCore® will be reviewed by the Helen Diller Family Comprehensive Cancer Center Site Committee on a weekly basis. The Site Committee will review and discuss at each weekly meeting the selected toxicity, the toxicity grade, and the attribution of relationship of the AE to the administration of the study drug(s).

All grade(s) 3-5 AEs entered into OnCore® will be reviewed on a monthly basis at the Site Committee meetings. The Site Committee will review and discuss the selected toxicity, the toxicity grade, and the attribution of relationship of the AE to the administration of the study drug(s).

In addition, all suspected adverse reactions considered "serious" entered into OnCore®, will be reviewed and monitored by the DSMC on an ongoing basis and discussed at DSMC meetings, which take place every six weeks.

Reporting to the Data and Safety Monitoring Committee

If a death occurs during the treatment phase of the study or within 30 days after the last administration of the study drug(s) and it is determined to be related either to the study drug(s) or to a study procedure, the Investigator or his/her designee must notify the DSMC Chair (or qualified alternate) within 1 business day of knowledge of the event. The contact may be by phone or e-mail.

Reporting to UCSF Institutional Review Board

The Principal Investigator must report events meeting the UCSF IRB definition of "Unanticipated Problem" (UP) within 10 business days of his/her awareness of the event.

Expedited Reporting to the Food and Drug Administration

If the study is being conducted under an IND, the Sponsor-Investigator is responsible for determining whether or not the suspected adverse reaction meets the criteria for expedited reporting in accordance with Federal Regulations (21 CFR §312.32).

The Investigator must report in an IND safety report any suspected adverse reaction that is both serious and unexpected. The Sponsor-Investigator needs to ensure that the event meets all three definitions:

- Suspected adverse reaction (as defined in Section 7.3.2.1)
- Unexpected (as defined in Section 7.3.2.2)
- Serious (as defined in Section 7.3.3)

If the AE does not meet all 3 of the definitions, it should not be submitted as an expedited IND safety report.

The timeline for submitting an IND safety report to FDA is no later than **15 calendar days** after the Investigator determines that the suspected adverse reaction qualifies for reporting (21 CFR 312.32(c)(1)).

Any unexpected fatal or life-threatening suspected adverse reaction will be reported to FDA no later than **7 calendar days** after the Investigator's initial receipt of the information (21 CFR 312.32(c)(2)).

Any relevant additional information that pertains to a previously submitted IND safety report will be submitted to FDA as a Follow-up IND Safety Report without delay, as soon as the information is available (21 CFR 312.32(d)(2)).

8 Statistical Considerations and Evaluation of Results

8.1 Study Endpoints

Primary endpoint: the proportion of patients with a >2 fold increase in the number of tumor infiltrating TILs cells per unit area (5 high power fields) post- vs. pre-pembrolizumab-based neoadjuvant treatment tumor specimens.

Secondary endpoints:

- **Safety:** An important secondary objective of this study is to characterize the safety and tolerability of pembrolizumab-based treatment in patients with resectable liver metastases. The safety analysis will be based on patients who experience toxicities as defined by NCI CTCAE 5.0 criteria (Appendix 3). Safety will be assessed by quantifying the toxicities and grades experienced by patients who have received pembrolizumab-based treatment, including all AEs and ECIs.

The attribution to drug, time-of-onset, duration of the event, its resolution, and any concomitant medications administered will be recorded. AEs will be analyzed including but not limited to all AEs, SAEs, and fatal AEs. Furthermore, specific immune-related AEs (irAEs) will be collected and designated as immune-related ECIs as described in Section 7.3.5.

Surgical complications will be characterized using Clavien-Dindo criteria (Appendix 4). Early stopping rules have been defined to mitigate risk of perioperative complications (see section 8.3).

- **Efficacy:** Endpoints for preliminary estimation of the clinical efficacy of pembrolizumab-based treatment in the perioperative setting for patients with CRC with resectable hepatic metastases are as follows:
 - Pathologic response rate [34]
 - R0 resection rate
 - 2-year RFS with and without adjuvant pembrolizumab-based therapy
 - Objective Response Rate

Exploratory endpoints:

- Change in T-cell repertoire in pre-neoadjuvant treatment liver biopsies vs. surgical tumor specimens as well as in blood samples from the same time-points
- Change in PD-L1 expression and other molecular markers in pre-neoadjuvant treatment liver biopsies vs. surgical tumor specimens
- Correlate changes in microbiome composition and diversity (by metagenomic sequencing and untargeted metabolomics of stool collected before, during, and after immunotherapy), with diet and lifestyle factors determined by self-reported questionnaires.
- Explore the correlation between change in tumor infiltrating TILs and T-cell repertoire.

8.1.1 Study Design

This is a single-site, single-arm, open-label Phase 2 clinical trial of pembrolizumab + vactosertib in patients with CRC with resectable hepatic metastases.

8.1.2 Randomization

This is a non-randomized study.

8.1.3 Stratification Factors

None. There are no planned patient stratification factors.

8.2 Determination of Sample Size and Accrual Rate**8.2.1 Sample Size and Power Estimate**

For the primary objective, there will be a binary classification (28). A patient will be considered to have a “positive response” if there is a ≥ 2 -fold increase (from pre- to post-treatment) in the number of TILs, and a “negative response” if there is < 2 -fold increase. Obtaining paired specimens from 17 patients will be sufficient to determine whether 40% or more achieve a “positive response,” compared to a null hypothesis of 10% or less. This comparison has a power of 0.91 at a significance level of 0.05 for a directional binomial test.

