3.2 Number of Patients

In order to accrue 17 patients who are evaluable for the primary endpoint, the plan is to enroll a total of 19 patients. If 2 or more of first 6 patients are unable to undergo planned surgical resection of their liver metastases in timely fashion (i.e., within 4-6 weeks of the final chemotherapy administration [if applicable]) or experience surgical complications attributed to pembrolizumab-based treatment, accrual will be suspended, and our strategy will be revisited.

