8.2.2 Replacement Policy

We plan to enroll 19 patients to achieve our goal of 17 patients evaluable for the primary study outcome. If more than 2 patients turn out not to be evaluable for the primary study outcome (i.e., do not have available post-pembrolizumab-based neoadjuvant treatment tumor tissue available for analysis), they may be replaced upon discussion with the study Principal Investigator and JSC.

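### Seventeen evaluable patients give exact power of 0.874, not 0.91, for the stated one-sided binomial test at 0.05, and no responder cut-off is given

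*Combined protocol and SAP*

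**What the plan says.** Section 8.2.1 classes each patient as a positive or negative responder according to whether TILs at least double from the pre-treatment to the post-treatment specimen. The sample size is set to test a null rate of at most 10% against an alternative of at least 40%, with 17 paired specimens. The power claim is: "This comparison has a power of 0.91 at a significance level of 0.05 for a directional binomial test". The section gives no number of positive responders that would count as success, no attained type I error, and no indication that the power is approximate.

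Sections 3.2 and 8.2.2 rest on the same target of 17. Section 8.2.2 says: "We plan to enroll 19 patients to achieve our goal of 17 patients evaluable for the primary study outcome". Those two sections make no power claim of their own.

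**The concern.** A binomial test on 17 patients can reject only at a whole number of responders, so its size and power move in steps. Only a few pairs of type I error and power are available, and 0.91 together with 0.05 did not look like one of them.

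This power statement is the only statistical justification for 17 evaluable patients. If it is too high, the chance of missing a true 40% response rate is understated. Because no cut-off is written down, the discrepancy cannot be seen in the text. Someone who takes 0.05 and 0.91 at face value could also read 4 of 17 as a positive result, when that rule has a one-sided error of 8.3%.

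**Working it through.** **Inputs, all from Section 8.2.1:** n = 17 paired specimens, null rate p0 = 0.10, alternative p1 = 0.40, level 0.05, one-sided binomial test. Nothing has to be assumed.

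**Step 1: reproduce 0.91.** The one-sided arcsine approximation is

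power = Φ(2[arcsin √p1 − arcsin √p0]√n − z0.95)

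- 2 × (0.6847 − 0.3218) = 0.7259
- 0.7259 × √17 = 2.993
- 2.993 − 1.645 = 1.348, and Φ(1.348) = 0.911

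This matches the plan's figure. Other routes:

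| Method, n = 17 | Power |
|---|---|
| Arcsine, one-sided 0.05 | 0.911 |
| Randomised binomial test at exactly 0.05 | 0.911 |
| Normal approximation, two-sided 0.05 | 0.907 |
| Normal approximation, one-sided 0.05 | 0.935 |
| Same, with continuity correction | 0.898 |

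The randomised test would declare 4 responders significant with probability (0.05 − 0.0221)/(0.0826 − 0.0221) = 0.46. That gives 0.8740 + 0.46 × (0.9536 − 0.8740) = 0.911. The two-sided route does not fit the directional test in the text.

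**Step 2: the test as stated.** For cut-off r, alpha is P(X ≥ r) with X ~ Bin(17, 0.10), and power is P(X ≥ r) with X ~ Bin(17, 0.40).

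- Null, P(X ≤ 4): 0.1668 + 0.3150 + 0.2800 + 0.1556 + 0.0605 = 0.9779, so alpha at r = 5 is 0.0221.
- Alternative, P(X ≤ 4): 0.0002 + 0.0019 + 0.0102 + 0.0341 + 0.0796 = 0.1260, so power at r = 5 is 0.8740.

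| Reject if at least | Alpha | Power at 40% |
|---|---|---|
| 4 | 0.0826 | 0.9536 |
| 5 | 0.0221 | 0.8740 |
| 6 | 0.0047 | 0.7361 |

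The best cut-off that respects 0.05 is 5. No whole-number cut-off gives 0.91. A mid-p value does not admit 4 responders either: it is 0.0524.

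**Step 3: size of the gap.** 0.91 − 0.874 = 0.036. The type II error is 1 − 0.874 = 0.126 against 1 − 0.91 = 0.09, and 0.126/0.09 = 1.40.

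**Step 4: other evaluable numbers, cut-off 5.**

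| Evaluable n | Alpha | Power at 40% |
|---|---|---|
| 15 | 0.0127 | 0.783 |
| 16 | 0.0170 | 0.833 |
| 17 | 0.0221 | 0.874 |
| 18 | 0.0282 | 0.906 |
| 19 | 0.0352 | 0.930 |
| 20 | 0.0432 | 0.949 |

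Five is the smallest admissible cut-off throughout this range. A cut-off of 4 already has alpha 0.0556 at n = 15, and a cut-off of 5 reaches 0.0522 at n = 21.

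**The case against.** The strongest reply is that 0.91 is a recognisable approximation and not a slip. The section is headed as an estimate and never calls the test exact. That explains where the figure comes from, but does not make it right for the test named. Only 17 × 0.10 = 1.7 responders are expected under the null, too few for a normal approximation to be reliable, and the text does not label the figure as approximate.

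Three further points stand, and they limit the finding:

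- A level of 0.05 is an upper bound. An attained 0.022 satisfies it, and is not a second fault.
- The loss is 3.6 points. Power stays above the conventional 0.80, the plan sets no minimum, and 18 or 19 evaluable patients would give 0.906 or 0.930. Seventeen is not shown to be inadequate.
- Section 8.4.1 already takes all patients with evaluable paired specimens into the primary analysis, so that part of the fix makes existing intent explicit.

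It can also be said that a cut-off in Section 8.2.1 will not govern the result by itself. Section 8.4.2 lists paired t and Wilcoxon tests on CD3+ T-cells and no binomial test, and Section 8.1 defines the endpoint as more than 2-fold where Section 8.2.1 has at least 2-fold. Both observations are correct, but they are separate issues and leave the power figure as wrong as before.

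**Conclusion.** The concern holds. Under the inputs and test that Section 8.2.1 states, the non-randomised binomial test rejects at 5 or more responders out of 17, with attained one-sided alpha 0.022 and power 0.874 at a true rate of 40%. The plan's 0.91 is an unlabelled approximation, or the power of a randomised test that is not described.

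The practical size is modest: a 12.6% chance of missing a true 40% rate instead of 9%. With the named test, power first passes 0.90 at 18 evaluable patients. The conclusion assumes exactly 17 evaluable patients and independent binary responses. The statement should be corrected, but the sample size need not change.

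**What to change.** Replace the power sentence in Section 8.2.1 with text such as:

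> With 17 evaluable patients, the null hypothesis is rejected if at least 5 have a ≥2-fold increase in TILs. The exact one-sided type I error is 0.022, and power is 0.87 at a true rate of 40%. The same cut-off of 5 applies for any evaluable number from 15 to 20 (type I error 0.013 to 0.043), and all evaluable patients up to the 19 planned are analysed. If all 19 are evaluable, power is 0.93.

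Merely labelling 0.91 as approximate would be a weaker remedy, because the decision rule would still be missing. Section 8.4.2 should refer to the same rule when its own mismatch with the endpoint is resolved.

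The cost is a few lines of text and a slightly less favourable power figure. Sections 3.2 and 8.2.2 keep their enrolment numbers.

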8.2.2 Replacement Policy

We plan to enroll 19 patients to achieve our goal of 17 patients evaluable for the primary study outcome. If more than 2 patients turn out not to be evaluable for the primary study outcome (i.e., do not have available post-pembrolizumab-based neoadjuvant treatment tumor tissue available for analysis), they may be replaced upon discussion with the study Principal Investigator and JSC.

8.2.3 Accrual estimates

Based on current estimates of the number of eligible patients seen at UCSF annually, as well as strong interest among patients in receiving immunotherapy, we anticipate completing accrual within 1 year.

8.3 Interim Analyses and Stopping Rules

The trial will be stopped early if 2 of the first 6 patients fail to undergo liver resection surgery within 6 weeks of their final chemotherapy treatment (if applicable) due to AEs attributed to pembrolizumab-based treatment, or experience Grade IV-V surgical complications according to Clavien-Dindo classification attributed to pembrolizumab -base treatment (Appendix 4).

Of particular significance to this study, enrolling patients being treated with curative intent, are perioperative complications attributed to pembrolizumab-based treatment. These may include delaying surgery due to pre-operative AEs and complications during or after surgery attributed to pembrolizumab-based treatment. Early stopping rules have been defined to mitigate risk of perioperative complications. The study will be stopped and the approach will be re-evaluated if 2 or more of the first 6 patients experience any one of the following:

- A delay in planned surgery beyond the 6-week window from final chemotherapy (if applicable), due to any grade toxicity attributable to study treatment. Delays in surgery due to other reasons (scheduling, available O.R time, patient preference) will not count.
- Grade IV and V surgical complications according to Clavien-Dindo classification (Appendix 4). *Note:* Surgical complications associated with liver metastectomy are very common, and we recognize that it may be difficult to attribute any such complications to preoperative administration of pembrolizumab. Therefore, the occurrence of such events may not necessarily require stopping the study early, but will be discussed amongst members of the JSC, with particular attention paid to specific complications such as liver failure, severe colitis, etc.

Enrollment will be paused for 4 weeks after the sixth patient undergoes surgery (or receives their last dose of pembrolizumab if unable to undergo surgery). During this interval the study investigators will meet with the participating surgeons to review the first 6 cases. A recommendation will be made regarding whether or not to enroll additional patients and if any changes are needed to optimize safety or feasibility.

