Study Drugs	
Neoadjuvant pembrolizumab will be administered at a fixed dose of 200 mg (IV) for 1 cycle plus 200 mg vactosertib (PO QD, 5 days per week x 2 weeks).
 
Adjuvant pembrolizumab (400 mg IV) + vactosertib (200 mg PO QD Cycle 1, 5 days per week, Cycles 2 and beyond 200 mg BID, 5 days per week) will be administered for up to eight 6-week cycles.

Phase 2, Pembrolizumab, Vactosertib

Safety Assessments	Safety assessments will include adverse events, clinical laboratory evaluations, and vital signs.
Efficacy Assessments	Objective response rate, pathologic response rate, R0 resection rate, and 1-year and 2-year RFS.
Unique Aspects of this Study	This is the first study to evaluate the safety and efficacy of pembrolizumab plus vactosertib following FOLFOX chemotherapy in patients with metastatic CRC undergoing liver resection with curative intent. Biopsy of a liver metastasis prior to administering pembrolizumab plus vactosertib and resection of the liver metastases following 1 cycle of pembrolizumab plus vactosertib will enable extensive scientific correlatives.

Study Schema

The above timeline is approximate with further guidelines below:

- A screening computed tomography (CT) chest/abdomen/pelvis with intravenous (IV) contrast must be performed and reviewed to confirm candidacy for hepatic resection prior to study entry.
- If chemotherapy is a direct lead-in to study enrollment, then liver resection surgery should be performed within 4-6 weeks of the final chemotherapy administration. During this 4-6 week window, 1 cycle of pembrolizumab plus vactosertib will be administered approximately 2 weeks (minimum 1 week) after the last dose of chemotherapy, and surgery will occur approximately 2 weeks (minimum 1 week) after C1D1.
- Labs, including liver function testing will be performed after C1D1, as close to surgery as possible.

Phase 2, Pembrolizumab, Vactosertib

- In the event that the surgery is canceled, and the first liver biopsy yielded adequate tumor material, a second liver biopsy will be requested (same lesion as the first biopsy preferred).
- Participants will be followed for up to 2 years after surgery or will be offered optional adjuvant treatment (described below).

Optional Adjuvant Treatment

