3.3.1 Inclusion Criteria

Patients are eligible for this trial if all of the following inclusion criteria are met:

1. Has histologically or cytologically confirmed CRC with liver metastases. In addition to liver metastases, extrahepatic metastases (e.g. pulmonary metastases) may be permitted if all

other eligibility criteria are met. Patients are permitted to have primary tumor *in situ* (Neoadjuvant Arm only).

2. Has received previous oxaliplatin-based chemotherapy.
 - a. FOLFOX or CapeOx does not need to be a direct lead-in to this study.
 - b. If chemotherapy is a direct lead-in to this study, concurrent mAb therapy (bevacizumab, cetuximab, or panitumumab) is acceptable, however the antibody must be omitted from the final cycle of chemotherapy prior to pembrolizumab.
3. Is an appropriate candidate to undergo liver biopsy and resection (\pm ablation) of liver metastases (Neoadjuvant Arm Only)
4. Is willing and able to provide written informed consent/assent for the trial. The patient may also provide consent for Future Biomedical Research. However, the patient may participate in the main trial without participating in Future Biomedical Research.
5. Is ≥ 18 years of age on day of signing informed consent.
6. Has measurable disease based on RECIST 1.1 as assessed by the investigator. Lesions situated in a previously irradiated area are considered measurable if progression has been demonstrated in such lesions. (Neoadjuvant Arm Only)
7. Is willing to provide tissue from a newly obtained core or excisional biopsy of a tumor lesion. Newly-obtained is defined as a specimen obtained after last dose of standard of care lead-in chemotherapy [if applicable] and within 28 days prior to first dose of pembrolizumab. (Neoadjuvant Arm Only)
8. Has a performance status of 0 or 1 on the Eastern Cooperative Oncology Group (ECOG) Performance Scale (Appendix 1).
9. Has adequate organ function as defined in Table 1, within 10 days of treatment initiation.

Table 1 Adequate Organ Function Laboratory Values

System	Laboratory Value
Hematological	
Absolute neutrophil count (ANC)	$\geq 1,500/\mu\text{L}$
Platelets	$\geq 100,000/\mu\text{L}$
Hemoglobin	$\geq 9 \text{ g/dL}$ or $\geq 5.6 \text{ mmol/L}$ without transfusion or erythropoietin (EPO) dependency (within 7 days of assessment)
Renal	

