5.1.4 Dose Limiting Toxicity

As the toxicities of pembrolizumab are well-established and not necessarily dose-dependent, this study will not use formal dose-limiting toxicity definitions according to NCI CTCAE grading criteria. However, to avoid compromising patient safety in this potentially curative setting, early stopping rules will be followed such that the study will be stopped, and this approach re-evaluated, if 2 or more of the first 6 patients experience any 1 of the following:

- A delay in planned surgery beyond the 8-week window after final chemotherapy treatment due to any grade toxicity attributable to study treatment. Delays in surgery due to other reasons (scheduling, available operating room time, patient preference) will not count.
- Grade IV and V surgical complications according to Clavien-Dindo classification (Appendix 4).

Note: Surgical complications associated with liver metastasectomy are very common, and we recognize that it may be difficult to attribute any such complications to preoperative administration of pembrolizumab-based treatment. Therefore, the occurrence of such events may not necessarily require stopping the study early, but will be discussed amongst members of the JSC, and Merck with particular attention paid to specific complications such as liver failure, severe colitis, etc.

Moreover, enrollment will be paused for 4 weeks after the sixth patient undergoes surgery (or receives their dose of pembrolizumab-based treatment if unable to undergo surgery). During this interval the study investigators will meet with the participating surgeons and Merck to review the first 6 cases. A recommendation will be made regarding whether or not to enroll additional patients and if any changes are needed to optimize safety or feasibility.

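### Patients without direct lead-in chemotherapy have no defined time limit for delayed surgery in the 2-of-6 stopping rule (8.3, 3.2), and 5.1.4 leaves it unclear how their delays count

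*Combined protocol and SAP*

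**What the plan says.** Prior oxaliplatin-based chemotherapy is required, but 3.3.1 (criterion 2a) states: "FOLFOX or CapeOx does not need to be a direct lead-in to this study". The Study Schema ties the surgical window to lead-in: "If chemotherapy is a direct lead-in to study enrollment, then liver resection surgery should be performed within 4-6 weeks of the final chemotherapy administration". Within that window, "1 cycle of pembrolizumab plus vactosertib will be administered approximately 2 weeks (minimum 1 week) after the last dose of chemotherapy".

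The rules that deal with delayed surgery are these:

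- **8.3, opening sentence:** early stopping when the following is true of two among the initial six: "fail to undergo liver resection surgery within 6 weeks of their final chemotherapy treatment (if applicable) due to AEs attributed to pembrolizumab-based treatment".
- **8.3, first bullet:** stop and re-evaluate if 2 or more of the first 6 have "A delay in planned surgery beyond the 6-week window from final chemotherapy (if applicable), due to any grade toxicity attributable to study treatment". Delays for scheduling, operating-room or patient-preference reasons are excluded.
- **3.2:** suspend accrual if 2 or more of the first 6 are "unable to undergo planned surgical resection of their liver metastases in timely fashion", explained as "within 4-6 weeks of the final chemotherapy administration [if applicable"].
- **5.1.4:** a near-copy of the 8.3 bullet, but reading "A delay in planned surgery beyond the 8-week window after final chemotherapy treatment due to any grade toxicity attributable to study treatment", with no applicability qualifier.
- **8.4.3, feasibility criterion (1):** at least 14 of 17 patients with R0 resection inside 6 weeks of the last chemotherapy, again only where that applies. This is descriptive.

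Table 10 schedules surgery 7-14 days after C1D1, and 5.1.3 puts it at about 2 weeks after the neoadjuvant dose, with a minimum of 1 week. None of the rules above refers to that schedule.

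**The concern.** Section 8.3 names surgery put off by pre-operative adverse events as one of the harms its stopping rule is meant to limit in patients treated with curative intent. The eligibility criteria and the schema were written to accommodate patients without lead-in chemotherapy. The rules were adapted only by adding a qualifier that removes the chemotherapy clock for those patients, and nothing was put in its place.

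With a threshold of two events in six patients, classifying a single patient differently can decide whether the rule is met. A predefined trigger should not depend on which section the study team consults, or on how it reads a parenthesis, once a delay has occurred.

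**Working it through.** No stated figure in the plan bears on this point, so the main check is textual. Take a patient whose last chemotherapy ended more than 8 weeks before the planned surgery date. Treatment-attributed toxicity postpones surgery, and surgery is then performed.

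| Rule | Reading | Does the delay count? |
|---|---|---|
| 8.3 opening | clock drops out | No: the patient did undergo surgery. Only a cancellation would count |
| 8.3 bullet | whole item does not apply | No |
| 8.3 bullet | only the 6-week figure does not apply | Yes, but no length is stated |
| 3.2 | clock drops out | Judgement: timeliness remains without a number |
| 5.1.4 | literal | Yes, at any length: the 8 weeks have already run out |
| 5.1.4 | qualifier omitted by oversight | As for the 8.3 bullet |

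The answer varies between and within sections, and no row supplies a number of days.

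**Illustration of size.** The documents give neither the delay risk nor the share without lead-in, so both are assumed. Let *d* be each patient's risk of a toxicity delay past the limit and *m* the number without lead-in among the first six, with patients independent. Only the delay limb is considered.

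P(at least 2 of *k*) = 1 − (1−d)^k − k·d·(1−d)^(k−1), with k = 6 − m if these patients are not counted and k = 6 if everyone has a limit.

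- d = 0.10, k = 6: 1 − 0.5314 − 0.3543 = 0.114
- d = 0.10, k = 5 (m = 1): 1 − 0.5905 − 0.3281 = 0.081
- d = 0.10, k = 3 (m = 3): 1 − 0.7290 − 0.2430 = 0.028
- d = 0.05, m = 1: 0.023 not counted, 0.033 all counted
- d = 0.20, m = 3: 0.104 not counted, 0.345 all counted

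If five or six of the first six lack lead-in and are not counted, the limb cannot reach two events.

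Under the literal 5.1.4 reading, those *m* patients count for any toxicity delay. With an assumed 20% risk of any such delay, and the lead-in patients kept at 10%, the chance is 0.147 for m = 1 and 0.222 for m = 3. These two figures hold only on that reading.

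**A limit from C1D1.** Section 8.3's 6 weeks is 42 days. Subtracting the usual 2-week gap between chemotherapy and C1D1 gives 42 − 14 = 28 days.

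**The case against.** The strongest reply is that the qualifier most naturally attaches to the 6-week window and not to the delay. Surgery has a planned date for every patient through Table 10 and 5.1.3, so a toxicity delay against that date would count, and 5.1.4 may simply omit a qualifier used elsewhere. On that view the sections can be reconciled. This stands to the extent that a contradiction between 8.3 and 5.1.4 is possible but not established. It does not supply a limit: Table 10 and 5.1.3 are scheduling targets that no rule cites, and the rule would then count a delay of any length for these patients while lead-in patients have a defined window.

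A second reply is that the flexibility is deliberate. Section 1.3 says it was built in because practice varies for metachronous disease. That explains the eligibility criterion but does not say how the stopping rule should treat those patients.

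A third is that other safeguards remain: the Grade IV-V limb, the 4-week pause and review after the sixth patient, the safety ground for termination in 6.8, and site committee review in 7.8. Section 6.1.4 also keeps surgery on schedule when vactosertib is held, barring safety concerns. This stands and limits the consequence. The six-case review, however, ends in a discretionary recommendation and comes only after the sixth patient, whereas the rule is a predefined trigger that could act earlier.

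A reader might go further and infer that the stopping rule is switched off for these patients. The documents do not support that: their complications count in full, and a cancellation because of adverse events arguably still falls under the 8.3 opening sentence and 3.2.

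**Conclusion.** The point holds in limited form. For patients without direct lead-in chemotherapy, 8.3 and 3.2 set no time limit for delayed surgery, and 5.1.4 leaves open whether and from when a toxicity delay counts. The gap concerns only toxicity-driven delay that still ends in surgery.

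Its size cannot be determined from the documents. Under the assumptions shown, leaving these patients uncounted lowers the chance of the delay limb reaching two events by about 1 percentage point at the small end (0.033 to 0.023) and about 24 points at the large end (0.345 to 0.104). The large end needs a 20% delay risk and half of the first six without lead-in. The textual gap does not depend on these figures.

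It would be tempting to conclude that the feasibility result is compromised as well. Under 8.4.3(1) a late R0 resection in such a patient would pass as a success, but the criterion is descriptive and no hypothesis test is affected. The 6-week versus 8-week difference between 8.3 and 5.1.4 is a separate matter and adds no weight here.

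**What to change.** In 8.3, 5.1.4 and 3.2, keep the chemotherapy clock for lead-in patients and add one limit from C1D1 for all others, for example: *surgery not done within 28 days of C1D1 owing to treatment-attributed toxicity*. State that such delays count toward the 2-of-6 rule. The surgeons should confirm the number, because 28 days is carried over from the lead-in timetable and allows twice the 14-day upper end of Table 10's surgery window. If the sponsor settles the separate mismatch in favour of 8 weeks, the same subtraction gives 56 − 14 = 42 days.

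For consistency, apply the same limit to these patients in 8.4.3(1), and report the interval from C1D1 to surgery.

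The cost is amendment wording in four sections. No new data are needed, since the C1D1 and surgery dates are already recorded. The downside is that the delay limb triggers somewhat more often than if these patients were left out: 0.114 against 0.081 with one of six, or against 0.028 with three of six, at an assumed 10% delay risk. Against the literal 5.1.4 reading it would trigger less often.
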